## 1 Introduction

This document is a protocol for a human research study. This study will be carried out in accordance with the applicable United States government regulations and Mayo Clinic research policies and procedures.

Each year, between 300,000 to 600,000 individuals suffer an acute venous thromboembolic event (1-4). These events primarily involve the deep veins of the lower extremities (deep vein thrombosis, DVT) which may lead to embolization to the pulmonary arteries (pulmonary embolism, PE). Deep vein thrombosis of the lower extremity is divided into two categories depending on the proximal extent of thrombosis. Thrombi involving the popliteal, femoral and iliac veins are categorized together into "proximal DVT" largely due to their increased embolic potential. Indeed, the risk of embolization of proximal DVTs may be as high as 50% (3). Whereas the risk of mortality associated with a PE is high, prompt identification and treatment initiation with anticoagulants is a medical emergency. Both the evaluation and management of proximal DVT and PE has been well established by randomized controlled trial data (5).

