Based on these treatment trials, guideline recommendations for patients with cDVT include a preference for serial ultrasound evaluation with observation over anticoagulation therapy in the absence of severe symptoms, active cancer, hospitalized status, prior history of VTE, unprovoked event, multiple venous involvement or large thrombus size ( $> 7$  mm width and or  $> 5$  cm length) or positive fibrin D-Dimer (5). This approach however has **several disadvantages**. **First**, if untreated patients participating in the randomized trials and cohort studies are combined, the anticipated event rate for untreated VTE is relatively high at 11.2% at 3 months (7,12,14,15,17). This includes a DVT propagation rate of 4.8%, PE rate of 1% and VTE recurrence rate of 5.4%. These event rates are high by comparison to patients with unprovoked

proximal DVT or PE. For unprovoked proximal DVT or PE, the event recurrence rate is approximately 8% at one year and 30% at 5 years. For these unprovoked VTE, there is universal agreement that continued anticoagulation therapy is indicated (Grade 1A) (5). If the latter deserves ongoing anticoagulant therapy then cDVT should deserve consideration for anticoagulant therapy as well. **Second**, the reason for avoiding anticoagulant therapy is said to be due to increased rate of major bleeding. In the CACTUS trial, this rate was acceptably low at 0.8% (15). In the trial by Ferarra et al, there were no major bleeding events despite enrollment confined to post-operative patients (13). **Third**, the post thrombotic syndrome following cDVT is said to be low however this has not been adequately studied and no firm conclusion can yet be established. **Fourth**, cDVT was specifically excluded from the recent large randomized trials of DOACs. **Fifth**, serial ultrasound does nothing for VTE prevention. Timing the interval to 7 days between studies may place the patient at considerable risk of thrombotic propagation and embolization which may prove to be a life threatening event. For these combined reasons, a prospective randomized trial of anticoagulant therapy compared to serial ultrasound imaging strategy is necessary and important. Given the vast number of patients suffering calf DVT each year in our society, establishing the most appropriate treatment strategy is paramount.

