### **3 Study Design**

#### **3.1 General Design**

This is a Single center, multi-Mayo site, randomized, double-blind, placebo-controlled, superiority clinical trial. Major bleeding and clinically relevant non-major bleeding will also be evaluated. Subjects will be screened at both outpatient clinic visit appointments or during hospitalization using direct referrals or by daily automated electronic screening of vascular radiology ultrasound and computed tomography reports. The baseline ultrasound will be clinical indicated, obtained for this purpose, and will be carefully reviewed by study personnel. Interested qualified subjects will be consented and offered participation in this trial. Pre-randomization anticoagulation treatment for cDVT is allowed up to a maximum of 72 hours. After randomization, patients allocated to apixaban will receive 10 mg twice daily for 7 days, followed by 5 mg twice daily for 3 months. Patients allocated to placebo control will receive twice daily matching placebo tablets in a similar fashion. All patients will undergo serial ultrasound imaging at 7 days, 14 days and 90 days. Patients developing symptomatic DVT or PE will be evaluated by cross-sectional imaging (ultrasound or computed tomography (CTA)) appropriate for their symptom assessment as part of their standard care. Allocation to treatment will be done centrally. Once consent has been obtained, clinically indicated baseline laboratory values will be confirmed (drawn within past 4 weeks) and subjects will begin treatment and follow-up for 3 months.

The primary composite efficacy endpoint of this study will be a composite of thrombus propagation, pulmonary embolism (PE), symptomatic VTE recurrence including recurrent DVT, PE or all cause fatality. The primary safety outcome will be major bleeding and clinically relevant non-major bleeding (ISTH criteria; 21). All suspected recurrent VTE, deaths, as well as all episodes of bleeding and vascular events will be evaluated by a central, blinded, independent adjudication committee. Adjudication results will be the basis for the final analyses.

There will be two secondary endpoints. The first will assess the timing of thrombus propagation relative to the original date of diagnosis for those individuals who experience a thrombus propagation. The second will be an assessment of net clinical benefit or harm assessed as the composite of the primary efficacy outcome or the principal safety outcome up to day 90.

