#### 6.2 Surveillance and Follow up.

Following randomization, subjects will be assigned to either active treatment with apixaban or placebo control for a total of 90 days. Each subject will then undergo follow up ultrasound imaging at 7 days (+/- 2 days), 14 days (+/- 2 days) and 90 days (+/- 7 days). This ultrasound imaging study will focus on venous thrombus propagation into the proximal venous segments. At each follow up, all venous segments of the involved lower extremity will be imaged. This imaging should be performed at a site participating in this research project. Patients will be called at Days 30 & 60 (+/- 7 days) to check their health status, adverse reactions and medication compliance.

Patients will be instructed to report to the clinic immediately if they had any bleeding or symptoms of recurrent deep-vein thrombosis, pulmonary embolism, or both. All suspected episodes of recurrent thrombosis will be investigated with the use of objective tests, according to prespecified diagnostic algorithms. At 3 months (+/- 7 days), patients will return for a routine clinically indicated ultrasound and clinical assessment.

Study Activity	Day 0	Day 7 (± 2 days)	Day 14 (± 2 days)	Day 30 (± 7 days)	Day 60 (± 7 days)	Day 90 (± 7 days)
Informed consent	X					
History	X					
Concurrent meds	X	X	X	X	X	X

Collect data from clinical physical exam (Ht, Wt, BSA, VS)	X					
Collect Lab Values (CBC, creatinine, ALT/AST) a	X a					
Adverse event evaluation		X	X	X	X	X
B-HCG	X b					
Drug dispensing and collection of any unused drug	X					X
Ultrasound c	X	X	X			X
Telephone survey (appendix A)				X	X	

a = Collect data from clinical testing in the last 4 weeks.

b = Women of child bearing potential only. If not done clinically in the last 2 weeks.

c = The baseline ultrasound will be requested and performed by the provider caring for the patient. This will be a clinically indicated study and will not be repeated for study purposes. This US will serve as the baseline imaging study for trial purposes.

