6. Have you started any new medications?

Yes

If yes, please list: \_\_\_\_\_

No

7. Have you had any new leg swelling?

Yes,

If yes, suggest that the patient see their medical provider

No

8. Have you had any new chest pain or shortness of breath?

Yes,

If yes, suggest that the patient see their medical provider

No

9. On a scale of 0 – 10, what is your current pain level for the involved leg with the blood clot?  
(circle one)

0      1      2      3      4      5      6      7      8      9      10

Do you have any questions for me?

Thank you for participating in our study.

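### Appendix A items 7 and 8 only suggest a provider visit for new leg swelling, chest pain or breathlessness, leaving out the urgency that section 6.2 sets for the same symptoms.

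*Combined protocol and SAP*

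**What the plan says.** Section 6.2 schedules the calls: "Patients will be called at Days 30 & 60 (+/- 7 days) to check their health status, adverse reactions and medication compliance". The schedule of activities in the same section places the telephone survey (Appendix A) at those two time points and also marks adverse event evaluation there.

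Item 7 of the script asks about new leg swelling. Item 8 asks: "Have you had any new chest pain or shortness of breath". Under both items the only instruction for a positive answer is "If yes, suggest that the patient see their medical provider".

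Section 6.2 gives two rules for the same kind of symptom. The first concerns the patient: "Patients will be instructed to report to the clinic immediately if they had any bleeding or symptoms of recurrent deep-vein thrombosis, pulmonary embolism, or both". The second concerns the work-up: "All suspected episodes of recurrent thrombosis will be investigated with the use of objective tests, according to prespecified diagnostic algorithms".

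Section 3.1 adds that patients who develop symptomatic DVT or PE are imaged in whatever way is "appropriate for their symptom assessment as part of their standard care".

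**The concern.** The script is what the caller has in hand when a symptom is disclosed. A patient who first mentions chest pain on a day 30 call has, for whatever reason, not acted on the standing instruction in 6.2. The call is the study's chance to repeat that instruction, and the script offers something milder: a suggestion, with no timing.

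The stake is patient safety. Allocation is 1:1 (section 5.4.2), so about half of those called are taking placebo with a confirmed thrombus. The protocol's own view of PE is that "prompt identification and treatment initiation with anticoagulants is a medical emergency" (section 1). Section 1.1 also says, of a 7-day gap between scans, that it "may place the patient at considerable risk of thrombotic propagation and embolization which may prove to be a life threatening event". That remark is about surveillance by ultrasound alone rather than telephone calls, so it serves here only to show how seriously the protocol takes the risk in untreated patients.

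**Working it through.** The plan gives no figure on this point, so the check is mainly a comparison of texts.

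**1. Script against section 6.2**

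| | Appendix A, items 7 and 8 | Section 6.2 |
|---|---|---|
| Strength | a suggestion | an instruction |
| Timing | none | immediate |
| Where to go | the patient's medical provider | the clinic |
| Work-up | not mentioned | objective tests, for suspected episodes |

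The clear gap is in strength and timing. The destination differs in wording, but the documents do not show that the two are different places: section 4.3 recruits from inpatients and from anticoagulation clinics at the three participating sites. The testing rule in 6.2 applies to suspected episodes, so it does not require a scan after every positive answer.

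**2. Does the answer reach anyone who can act?** Yes, by a general route.
- Section 8.1 counts an unfavorable, unintended symptom as an adverse event.
- The 6.2 schedule has adverse events evaluated at days 30 and 60.
- Section 8.2 requires information on adverse events to be sought at each contact and recorded immediately.
- Section 8.3 has the study team take protective action, and has the sponsor-investigator evaluate the event and decide on follow-up.

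None of these sets a time limit for the evaluation, and the script does not refer to them.

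**3. Where the calls fall in follow-up.** Inputs are the visit days and windows in section 6.2.
- Day-14 visit to day-90 visit: 90 − 14 = 76 days.
- Shortest with windows: (90 − 7) − (14 + 2) = 67 days.
- Longest with windows: (90 + 7) − (14 − 2) = 85 days.
- Scheduled study contacts inside that span: two, the calls at days 30 and 60.

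**4. How often PE is expected.** Inputs are 125 placebo patients and a PE rate of 0.5% (section 7.1) or 1% (section 1.1).
- 125 × 0.005 = 0.625, about 0.6 cases.
- 125 × 0.01 = 1.25, about 1.3 cases.

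These counts cover the full three months, including the first two weeks, before any call. The number first disclosed at a call must be smaller or equal, and it cannot be derived from the documents.

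**The case against.** The strongest reply is that nothing here is broken. Section 6.2 gives patients a standing instruction, the script does not withdraw it, and both can be followed. Referral to the treating provider is a route the protocol itself uses: section 3.1 places imaging of symptomatic events within standard care, and section 4.4.2 has the treating provider start the alternative anticoagulant. Sections 8.2 and 8.3 bring the symptom to the sponsor-investigator in any case, and a sensible coordinator would escalate chest pain unprompted. PE should be rare, and leg swelling is non-specific in patients with a known calf DVT.

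Most of this stands. It rules out two stronger readings that a reader might infer:
- **That the script contradicts 6.2.** It does not. It is weaker advice given alongside a rule that still applies.
- **That a positive answer reaches nobody able to judge it.** The adverse event route in step 2 of the working does name a decision-maker. What it lacks is a deadline.

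The reply does not justify the wording itself. The general duties in section 8 give no timing for these symptoms, and the line the caller reads is an explicit instruction that falls short of the protocol's own standard.

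**Conclusion.** The point holds as a mismatch of urgency. For possible DVT or PE symptoms disclosed at the day 30 and day 60 calls, the script's response is milder than section 6.2, and the adverse event route behind it has no time limit. It is a cheap improvement for patient safety, of minor severity.

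Its practical size cannot be stated. A reader might take the 76-day span as a possible delay, or infer missed endpoint events or lost power. The documents support neither. The span measures the spacing of visits rather than the time from symptom to work-up. Unscheduled contact remains open throughout, and nothing in the documents says how many events would first surface at a call. Sample size, alpha and analysis are unaffected.

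The conclusion assumes that callers follow Appendix A as written and that no separate working instruction, outside these documents, already tells them to escalate.

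**What to change.** Replace the instruction in each item.
- **Item 8:** *If yes, tell the patient to report to the clinic or emergency department immediately, and notify the site investigator the same day.*
- **Item 7:** *If yes, tell the patient to report to the clinic promptly per section 6.2, and notify the site investigator the same day.*

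In both items, add that the investigator decides whether this is a suspected recurrence needing objective testing under 6.2. The caller should not be asked to judge whether a symptom is explained. The two items differ in tone because swelling is the less specific symptom here.

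The cost is a short edit to two script items, with no new form fields. It also takes a little coordinator and investigator time and leads to some extra symptom-driven assessments, mostly for leg swelling.

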## Appendix B1. Case Report Form; Initial data

Date Completed: \_\_\_\_\_ Completed By: \_\_\_\_\_

Name: \_\_\_\_\_

Birth date: \_\_\_\_\_

Gender: 1  Female 2  Male

Height (cm): \_\_\_\_\_

Weight (kg): \_\_\_\_\_

**Qualifying Event: Has the patient had a documented calf DVT confirmed by imaging? (check one)**

1  Yes 2  No If yes: Date diagnosed: (mm/dd/yyyy) \_\_\_\_/\_\_\_\_/\_\_\_\_\_

### Location of the DVT

Leg involved (check one) 1  Right 2  Left 3  Bilateral

Lower extremity deep vein involved (check all that apply and provide length of thrombus in cm)

1  Posterior Tibial Length \_\_\_\_\_ cm

2  Peroneal Length \_\_\_\_\_ cm

3  Anterior Tibial Length \_\_\_\_\_ cm

4  Gastrocnemius Length \_\_\_\_\_ cm

5  Soleal Length \_\_\_\_\_ cm

Was there evidence of proximal vein involvement (popliteal, femoral, ilial vein) 1  Yes 2  No

How was the thrombus confirmed? 1  Ultrasound 2  CT 3  MRI

### Pain assessment

On a scale of 0 – 10, what is your current pain level for the involved leg with the blood clot? (circle one)

0      1      2      3      4      5      6      7      8      9      10

### Clinical Characteristics

No identified risk factors (unprovoked, check one) 1  Yes 2  No

Surgery (within past 3 months) (check one) 1  Yes 2  No

Trauma (within past 3 months) (check one) 1  Yes 2  No

Travel > 6 hrs (within past 3 months) (check one) 1  Yes 2  No

Prior personal history of VTE (check one) 1  Yes 2  No

Family history of VTE (check one) 1  Yes 2  No

Estrogen therapy (check one) 1  Yes 2  No

Postpartum (within 6 weeks of delivery) (check one) 1  Yes 2  No

Hospitalization (within past 3 months) (check one) 1  Yes 2  No

Past Cancer history (check one) 1  Yes 2  No

Known thrombophilia (check one) 1  Yes 2  No

Describe \_\_\_\_\_

Inflammatory bowel disease (check one) 1  Yes 2  No

### Laboratory Data

Date collected (mm-dd-yr): \_\_\_\_ - \_\_\_\_ - \_\_\_\_

CBC: Hgb \_\_\_\_\_ WBC \_\_\_\_\_ Platelet \_\_\_\_\_

Creatinine: \_\_\_\_\_ ALT: \_\_\_\_\_ AST: \_\_\_\_\_

Smoking status (*check one*) 1active smoker 2former smoker 3never smoker

## Appendix B2. Case Report Form; Follow up data

Date Completed: \_\_\_\_\_

Completed By: \_\_\_\_\_

Circle One: Day 7 Day 14 Day 30 Day 60 Day 90 Day 365

Lower extremity deep vein involved (check all that apply and provide length of thrombus in cm)

1  Posterior Tibial	Length _____ cm
2  Peroneal	Length _____ cm
3  Anterior Tibial	Length _____ cm
4  Gastrocnemius	Length _____ cm
5  Soleal	Length _____ cm

Was there evidence of DVT propagation confirmed by imaging? (check one) 1  Yes 2  No

If yes, which veins were involved (check all that apply)?

- 1  Popliteal
- 2  Femoral
- 3  Iliac
- 4  IVC

### Pain assessment

On a scale of 0 – 10, what is your current pain level for the involved leg with the blood clot? (circle one)

0 1 2 3 4 5 6 7 8 9 10

Has patient had a documented recurrent venous thrombosis confirmed by imaging? (check one)

1  Yes 2  No

If yes: Date diagnosed: (mm/dd/yyyy) \_\_\_\_/\_\_\_\_/\_\_\_\_

Pulmonary Embolism (check one) 1  Yes 2  No

Lower extremity deep vein thrombosis (check one) 1  Yes 2  No

Upper extremity deep vein thrombosis (check one) 1  Yes 2  No  
(jugular, innominate, subclavian, axillary, brachial)

Splanchnic vein thrombosis (check one) 1  Yes 2  No  
(hepatic, portal, splenic, mesenteric, renal, gonadal)

Cerebral vein thrombosis 1  Yes 2  No

Fatal PE: (check one) 1  Yes 2  No

Was the VTE recurrence: (check one) 1  Symptomatic 2  Incidental

How was the thrombus confirmed?

1  Ultrasound 2  CT 3  MRI 4  VQ scan 5  Surgery 6  Autopsy

Arterial clot: (check one) 1  Yes 2  No

If Yes, (check all that apply)  MI  
 TIA/Stroke  
 Peripheral embolism

Has patient had a major bleed? (check one) 1  Yes 2  No

If Yes, date of major bleed: (mm/dd/yyyy) \_\_\_\_/\_\_\_\_/\_\_\_\_-\_\_\_\_

If Yes (check all that apply)  Intracranial (intracerebral (hemorrhagic stroke), subarachnoid, subdural)

Intraspinal/epidural

Intraocular

Intraarticular

Intramuscular with compartment syndrome

Retroperitoneal

Pericardial

Fatal bleeding

GI

GU

Pulmonary

Other Specify: \_\_\_\_\_

Has patient had a clinically relevant non-major bleed? (check one) 1  Yes 2  No

If Yes, date of clinically relevant non-major bleed: (mm/dd/yyyy) \_\_\_\_/\_\_\_\_/\_\_\_\_-\_\_\_\_

If Yes, what were the consequences (check all that apply)

Required medical intervention

Unscheduled contact with health care team

Temporary cessation of study treatment

Has patient had a minor bleed? (check one) 1  Yes 2  No

If Yes, date of minor bleed: (mm/dd/yyyy) \_\_\_\_/\_\_\_\_/\_\_\_\_-\_\_\_\_

Last Date (any modality of) protocol therapy was given: (mm/dd/yyyy) \_\_\_\_/\_\_\_\_/\_\_\_\_-\_\_\_\_  
(date of last treatment dose on this study or date decision made to stop protocol treatment)
